### 4.3 VARIATION FROM SCHEDULED VISIT DAYS

To allow for scheduling flexibility, limited variation will be permitted from the specified time of each visit (Table 2).

**Table 2: Allowed Variation from Scheduled Visit Days** 

Scheduled Visit	Allowed Variation	
Week 1	+ 2 days	
Weeks 2, 4, 8, 12, 16, 20, 24, 28, 32, and 36	+/- 3 days	

### 4.4 SCHEDULE OF VISITS AND PROCEDURES

A schedule of visits and procedures is provided in Appendix J.

### 4.5 SAFETY ASSESSMENTS

### 4.5.1 CLINICAL LABORATORY DATA

As outlined in Table 3, non-fasting samples for hematology, chemistry, PT and urinalysis will be collected at Screening, Week 4, and at the Final Evaluation Visit.

Blood and

urine will be collected using applicable safety precautions and will be processed according to the central clinical laboratory's instructions. Urinalysis will be evaluated at the trial center using supplies provided by the sponsor.

**Table 3: Clinical Laboratory Tests** 

Serum Chemistry	Hematology	Urinalysis	Additional Tests
Glucose Total bilirubin Alanine aminotransferase Aspartate aminotransferase Alkaline phosphatase Blood urea nitrogen	Hemoglobin Hematocrit Leukocyte Count (total) Leukocyte Count (differential) Red Blood Cell Count Platelet Count	Specific gravity pH Glucose Protein Blood Bilirubin Ketones	Prothrombin time (PT) (Screening, Week 4 and Final Evaluation only) Urine Pregnancy (WOCBP only)*

\*If positive at timepoints after study treatment, confirm by serum pregnancy test

It is the Investigator's responsibility to review the results of all laboratory tests as they become available. For each laboratory test result outside the reference range, the Investigator must ascertain if the abnormal lab result is a clinically significant result for that individual subject. Likewise, if laboratory tests are taken at follow-up visits, the

Investigator must ascertain if this is an abnormal and clinically significant change pretreatment for that individual subject. The Investigator may repeat the laboratory test or request additional tests to verify the results of the original laboratory test. The Investigator must sign and date all written laboratory results (e.g., urinalysis, hematology, chemistry, PT, and pregnancy tests) and note Not Clinically Significant (NCS) or Clinically Significant (CS) for each out of range laboratory value. If a laboratory value is determined to be a clinically significant result for that subject, this may be considered an AE. Refer to Section 6.1.1 for further information.

### 4.5.2 PREGNANCY TESTING

All WOCBP will have a UPT at the Screening Visit, Treatment Visit pre-treatment, and Final Evaluation Visit or Early Discontinuation, if applicable. If any result is positive prior to treatment, the subject will not be allowed to participate. The results of the UPTs for WOCBP will be evaluated at the trial center. Refer to Section 4.1.1 for further information

### 4.5.3 VITAL SIGNS

Vital signs (i.e., body temperature, respiration rate, sitting radial pulse rate, and sitting systolic and diastolic blood pressures) will be obtained at the Screening and Treatment Visit (pre- and post-treatment), Week 2, Final Evaluation or Early Discontinuation Visits and at any visit where signs or symptoms of botulinum toxicity is reported.

## 4.5.4 PHYSICAL EXAMINATION

A physical examination, in addition to vital signs, general appearance, skin, neck (including thyroid), eyes, ears, nose, throat, heart, lungs, abdomen, lymph nodes, and extremities will be conducted at Screening, Week 2 and Final Evaluation or Early Discontinuation Visits. Significant physical examination findings that are present prior to investigational product administration are to be included on the Medical History page.

Significant physical examination findings which meet the definition of an adverse event will be recorded on the adverse event page post-treatment.

### 4.5.5 12-LEAD ECG

At Screening and Week 4, a single standard supine 12-Lead ECG will be obtained after a subject has rested quietly for at least 10 minutes using equipment provided from the central reader. The ECG data will be submitted to a central reader for measurement.

## 4.5.6 INJECTION SITE EVALUATION

Injection sites will be evaluated at the Screening Visit, Treatment Visit pre- and post-treatment (to determine if there is an immediate reaction to the investigational product), Follow-up Visits, and Final Evaluation Visit or Early Discontinuation Visit, if applicable. The assessment will be done as a global evaluation of the 5 injection sites (Table 4).

[figure not shown]
**Table 4: Injection Site Evaluation** 

[figure not shown]
Assessment Descriptor	Pres	Present?	
	Yes	No	
Erythema			
Edema			
Burning or Stinging (sensation as described by subject)			
Itching (sensation as described by subject)			
Bruising			

[figure not shown]

[figure not shown]

#### 4.5.10 ADVERSE EVENTS

Adverse Events (AEs) will be graded as mild, moderate, or severe as defined in Section 6.1.2 of this protocol.

AEs will be evaluated at the Treatment Visit post-treatment, Follow-up Visits, and Final Evaluation Visit or Early Discontinuation Visit, if applicable. Section 6 outlines the procedures for recording and reporting AEs.

#### 4.6 EFFICACY ASSESSMENTS

#### 4.6.1 PRIMARY AND SECONDARY EFFICACY ASSESSMENTS

Efficacy assessments will include investigator assessment of glabellar line severity and glabellar line improvement, subject assessment of glabellar line severity and improvement. Efficacy assessments will be conducted with the subject in a sitting position. In order to have consistent eye positioning during the assessment, the investigator should ask the subject to focus on a fixed point in the examination room. The assessment should be conducted in a room with good overhead lighting or natural light from a window (but not direct sunlight).

## 4.6.1.1 Patient Frown Wrinkle Severity (PFWS)

At each clinic visit as designated in the Schedule of Trial Assessments (Appendix J), the subject will assess the visual appearance (at maximum frown and at rest after maximum frown) of the glabellar lines using the following 4 point scale for subject's assessment of Patient Frown Wrinkle Severity (Appendix B, Table 9). The assessment form will be provided directly to the subject to complete while reviewing the glabellar treatment area using a handheld mirror as outlined in Appendix B. Subjects with contact lenses should view their glabellar lines with contacts. Subjects wearing glasses should be advised to view their glabellar lines without glasses if possible. If glasses are needed for the subject to see their glabellar lines, then glasses can be worn for the assessment. The subject assessment must be completed before the Investigator completes the IGA-FWS assessment.

**Table 9: Patient Frown Wrinkle Severity** (PFWS)

Rating Score	Frown Wrinkle Severity	Description
0	None	No wrinkles
1	Mild	Very shallow wrinkles
2	Moderate	Moderate wrinkles
3	Severe	Deep wrinkles

## 4.6.1.2 Investigator Global Assessment Frown Wrinkle Severity

At each clinic visit as designated in the Schedule of Trial Assessments (Appendix J), the Investigator will assess the visual appearance (at maximum frown and at rest after maximum frown) of the glabellar lines using the IGA-FWS with the following 4 point scale (Table 10).

**Table 10: Investigator Global Assessment Frown Wrinkle Severity** (IGA-FWS)

Rating Score	Frown Wrinkle Severity	Description
0	None	No wrinkles
1	Mild	Very shallow wrinkles
2	Moderate	Moderate wrinkles
3	Severe	Deep and furrowed wrinkles

# 4.6.1.3 Global Aesthetic Improvement Scale

The Investigator and subject will assess the visual appearance (at maximum frown and at rest after maximum frown) of the glabellar line improvement from the baseline condition using the following 7 point severity Global Aesthetic Improvement Scale (GAIS, Table 11). Assessments will be made at the visits as designated in the Schedule of Trial Assessments (Appendix J).

The Patient GAIS assessment form (Appendix E) will be provided directly to the subject to complete while reviewing the glabellar treatment area (at maximum frown and at rest after maximum frown) using the supplied handheld mirror as outlined in Appendix E. Subjects with contact lenses should view their glabellar lines with contacts. Subjects wearing glasses should be advised to view their glabellar lines without glasses if possible.

If glasses are needed for the subject to see their glabellar lines, then glasses can be worn for the assessment. The subject assessment must be completed before the Investigator completes the IGA-FWS assessment.

**Table 11: Global Aesthetic Improvement Scale** 

Rating Score	Wrinkle Improvement
-3	Very Much Worse
-2	Much Worse
-1	Worse
0	No Change
1	Improved
2	Much Improved
3	Very Much Improved

[figure not shown]
#### 4.6.2 ADDITIONAL ASSESSMENTS

## 4.6.2.1 Subject Diary

At Day 0, subjects will be provided a paper diary Appendix D for the initial 2-week post treatment period to capture their assessment of the appearance of the lines at maximum frown using the 4 point severity scale. Subject's assessment of glabellar line severity is described above in Section 4.6.1.1, Table 9. Instructions on how to complete the diary will be provided with the diary to the subjects.

[figure not shown]
## 4.6.2.2 Subject Global Satisfaction with Treatment Questionnaire

The subject will be asked to provide a rating of their satisfaction with the treatment results at the Week 4 visit. Following the subject's completion of the Patient GAIS, the subject will be given a questionnaire to rate their satisfaction with the treatment results. Subjects will be asked how satisfied or dissatisfied they are with how the treated area of the face looks (Appendix F).

## 4.6.2.4 Facial Age Self Evaluation (FASE)

At each clinic visit designated in the Schedule of Trial Assessments (Appendix J), the subject will be asked to rate their perceived age on a FASE questionnaire (Appendix H). Following the subject's completion of the Patient GAIS, the subject will be given a questionnaire to rate their perception of how old they think they look following the treatment. Subjects will be asked how old they think they look post treatment in order to evaluate the psychological impact.

#### 4.7 SCREEN FAILURES

A screen failure subject will be a person from whom informed consent is obtained and is documented in writing (i.e., subject signs an informed consent form), but who does not meet the study eligibility requirements.

[figure not shown]
## 4.8 PROTOCOL DEVIATIONS

[figure not shown]
This trial will be conducted as described in this protocol, except for an emergency situation in which the protection, safety, and well-being of the subject requires immediate intervention, based on the judgment of the Investigator (or a responsible, appropriately trained professional designated by the Investigator). In the event of a significant deviation from the protocol due to an emergency, accident, or mistake, the Investigator or designee must contact Revance at the earliest possible time by telephone. This will allow an early joint decision regarding the subject's continuation in the trial. This decision will be documented by the Investigator and the Sponsor.

## 5 PROHIBITED THERAPIES AND MEDICATIONS

## 5.1 CONCOMITANT MEDICATIONS

Concomitant medications are any prescription or over-the-counter preparations used by subjects during participation in the trial. Use of concomitant medications will be recorded on the Concomitant Medications case report form (CRF) beginning at the Screening Visit until the Final Evaluation Visit. The dose and dosing regimen of all prescription and non-prescription therapies and medications, including herbs, vitamins, or other nutritional supplements administered will be documented.

#### 6 EVALUATION OF ADVERSE EVENTS

#### 6.1 **DEFINITIONS**

For this protocol, an adverse event (AE) is any untoward medical occurrence (e.g., sign, symptom, disease, syndrome, intercurrent illness, clinically significant abnormal laboratory finding, injury or accident) that emerges or worsens following administration of investigational product and until the end of trial participation that may not necessarily have a causal relationship to the administration of the investigational product. An AE can therefore be any unfavorable and/or unintended sign (including a clinically significant abnormal laboratory result), symptom, or disease temporally associated with the use of an investigational product, whether or not considered related to the investigational product. A treatment-emergent AE is one that occurs after any period of exposure to treatment.

Pre-existing conditions, which increase in frequency or severity or a change in nature as a consequence of an investigational product use will also be considered an adverse event.

An unexpected AE is an adverse reaction, the nature or severity of which is not consistent with the applicable product information (e.g., Investigator's Brochure for an unapproved investigational product or package insert/summary of product characteristics for an approved product).

Any clinically significant change in the study safety evaluations, (e.g., vital signs,	
injection site evaluation,	
post-treatment must be reported as an AE.	

A serious adverse event (SAE) is any untoward medical occurrence that results in any of the following outcomes:

- Death
- Life-threatening, (i.e., the subject was, in the opinion of the Investigator, at immediate risk of death from the event as it occurred. It does not apply to an AE that hypothetically might have caused death if it were more severe)
- Persistent or significant disability/incapacity or substantial disruption of the subject's ability to carry out normal life functions
- Requires in-patient hospitalization or prolongs hospitalization (i.e., a prolonged hospitalization beyond the expected length of stay; hospitalizations for elective medical/surgical procedures, scheduled treatments, or routine check-ups are not SAEs by this criterion)
- Congenital anomaly/birth defect (i.e., an adverse outcome in a child or fetus of a subject exposed to the molecule or investigational product before conception or during pregnancy)

• Does not meet any of the above serious criteria but based upon appropriate medical judgement may jeopardize the subject or may require medical or surgical intervention to prevent one of the outcomes listed above (i.e., is a significant or important medical event)

### 6.1.1 CLINICAL LABORATORY CHANGES

It is the Investigator's responsibility to review the results of all laboratory tests as they become available. For each laboratory test result outside the reference range, the Investigator must ascertain if the abnormal lab result is a clinically significant result for that individual subject. This determination, however, does not necessarily need to be made the first time an abnormal value is observed; the Investigator may repeat the laboratory test or request additional tests to verify the results of the original laboratory test. If this laboratory value is determined to be a clinically significant result for that subject, this may be considered an AE to be assessed according to severity.

The Investigator must sign and date all written laboratory reports (e.g., urinalysis, hematology, chemistry, PT, and pregnancy tests) and note Not Clinically Significant (NCS) or Clinically Significant (CS) for each out of range laboratory value.

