### **Safety Evaluations:**

• Clinical laboratory tests (hematology, chemistry, prothrombin time [PT], urinalysis)

 Name of Sponsor/Company:
 Revance Therapeutics, Inc.

 Name of Finished Product:
 DaxibotulinumtoxinA for Injection

 Name of Active Ingredient:
 daxibotulinumtoxinA

• Injection Site Evaluation

- 12-lead ECG
- Concomitant medications
- Collection of AEs
- Vital Signs
- Physical Examination

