## **Safety Endpoints**:

- Frequency, severity and relationship to study drug of treatment-emergent adverse events during the first four weeks post treatment and the overall study duration
- Frequency, severity and relationship to study drug of treatment-emergent serious adverse events during the first four weeks post treatment and the overall study duration

[figure not shown]

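### Section 6.1 makes a clinically significant post-treatment laboratory finding an AE, but Sections 4.5.1 and 6.1.1 make it optional, so sites may record the same result differently

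*Protocol*

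**What the plan says.** Two parts of the protocol bear on whether a laboratory result becomes an AE.

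**The definition (Protocol 6.1).** Among its named examples of an AE is a "clinically significant abnormal laboratory finding, injury or accident) that emerges or worsens following administration of investigational product". A later sentence in the same section says that any clinically significant change in the study safety evaluations "post-treatment must be reported as an AE". The list of examples in that sentence is partly blacked out; vital signs and the injection site evaluation can be read.

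**The laboratory review instructions (Protocol 4.5.1 and 6.1.1).** Below Table 3, Section 4.5.1 says: "If a laboratory value is determined to be a clinically significant result for that subject, this may be considered an AE". Section 6.1.1 repeats this with "this may be considered an AE to be assessed according to severity". In both sections the optional wording comes after the investigator has already judged the value clinically significant (CS). Neither section says when a CS value would not be an AE.

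**What depends on it.** Laboratory samples "will be collected at Screening, Week 4, and at the Final Evaluation Visit" (Protocol 4.5.1), which gives two post-treatment draws. The first safety endpoint is "Frequency, severity and relationship to study drug of treatment-emergent adverse events during the first four weeks post treatment and the overall study duration" (Protocol 7.3; SAP 3.3.1 has the same endpoint).

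**The concern.** An investigator who works from Section 6.1 must enter a new CS value at Week 4 as an AE. An investigator who works from Section 6.1.1, the paragraph on reviewing and signing laboratory reports, may mark the same value CS and enter nothing on the AE form. Both would be following the protocol.

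The stake is the TEAE endpoint. A result left off the AE form is not in the TEAE tables for the first four weeks or for the whole trial. No severity grade or causality assessment is required for it, because Section 6.1.2 asks for these on AEs only. The TEAE count then depends partly on which paragraph a site follows.

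**Working it through.** The plan states no figure on this point, so there is none to reproduce. The check is a comparison of the texts, followed by a simple scale calculation.

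**Step 1: do the two rules cover the same event?** Take a Week 4 value that the investigator judges CS.
- Under 6.1 it is an AE if it emerged or worsened after dosing.
- Section 4.2.1 requires every abnormal Screening result to be judged not clinically significant before randomization. In a correctly randomized subject, a CS value at Week 4 is therefore a change in the investigator's judgement since Screening, which will ordinarily mean new or worse.
- Section 4.5.1 expressly includes tests taken at follow-up visits, so its optional wording reaches this same value.

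**Step 2: does the mandatory sentence in 6.1 reach laboratory tests?** Its example list is partly redacted, so it cannot be said to name them. It is an open list of examples, however, and the synopsis puts clinical laboratory tests first under Safety Evaluations. Inclusion is a fair inference. The definition in 6.1 is enough without it.

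**Step 3: does any other text settle the matter?**
- Protocol 6.2 requires recording of AEs that the subject reports. That does not decide what happens to a laboratory finding.
- Protocol 7.6.1 and SAP 3.3.1 define treatment-emergent by onset alone.
- SAP 4.8.4.1 leaves clinical significance to each investigator and has no rule turning a CS result into an AE.
- By contrast, Protocol 4.5.4 gives physical examination a definite rule: findings that meet the AE definition go on the AE page. Laboratory results have no such sentence.

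No visible text resolves the difference.

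**Step 4: what would still be reported?** For a CS result not entered as an AE:
- listings of out-of-range and CS results (Protocol 7.6.2, SAP 4.8.4.1);
- summaries at Screening, Week 4 and Final Evaluation, with changes from Screening for continuous tests (SAP 4.8.4.1);
- shift tables for Screening and Final Evaluation, but not Week 4 (SAP 4.8.4.1);
- for urinalysis, counts by arm of abnormal, clinically significant results (SAP 4.8.4.1);
- follow-up to resolution or stabilization if the result arises at the final assessment (Protocol 6.5.1).

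What is lost is the entry in the AE tables and the severity and causality grades.

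**Step 5: scale.** Inputs: 200 active and 100 placebo subjects (Protocol Table 1 and Section 7.7).
- One subject whose only event is such a value: 1/200 = 0.5 percentage points on active; 1/100 = 1.0 point on placebo.
- The rate of such subjects is not given. Assume 1% to 5%. On active that is 200 × 0.01 = 2 to 200 × 0.05 = 10 subjects; on placebo, 100 × 0.01 = 1 to 100 × 0.05 = 5. TEAE incidence in an arm would then differ by 1 to 5 points between recording all of these results and recording none.
- Those are the two extremes. If a fraction *r* is recorded, and *p* is the share of subjects with such a value as their only event, the arm's incidence falls short by (1 − *r*) × *p*. If *r* and *p* are the same in both arms, the shortfalls cancel in the difference between arms.

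**The case against.** The strongest reply is that the texts can be read together. Section 6.1.1 is a subsection of 6.1 and covers all laboratory results, including those from Screening, which cannot be AEs. On that reading *may* means only that a CS value is an AE if it meets the parent definition. Section 6.1 also has a softer sentence, saying what an AE *can* be. This deserves weight, but neither 4.5.1 nor 6.1.1 states the restriction, 4.5.1 covers follow-up tests, and Section 4.2.1 leaves little room for CS values at Screening. If *may* was meant to avoid entering a laboratory sign of an AE already recorded, the text does not say that either.

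The objections on impact stand. Investigators, site staff and subjects are blinded, so uneven recording should be mostly non-differential between arms. Safety analysis is descriptive, and the primary endpoint is not touched.

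A reader might infer three stronger things that the documents do not support:
- **That unrecorded results surface only in a laboratory listing.** Step 4 shows that the SAP plans more than that.
- **That a definite share of laboratory AEs would be lost, or that the rate of some AE term would be halved.** The documents give neither a rate of CS results nor the share of sites using the optional wording, and *may* does not mean that such a site records none. CS values spread over the many tests in Table 3 would not form one AE term.
- **That no data check would catch this.** Protocol 9.1 plans checks for consistency and completeness with queries to sites. Their detail is not in these documents, so a check for this case cannot be called absent.

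**Conclusion.** The point holds as an inconsistency between Section 6.1 and Sections 4.5.1 and 6.1.1 of the current protocol. The definition makes a new or worsened CS laboratory finding an AE; the review instructions make the same result optional and give no criterion. Sites can record it differently, and unrecorded results would be missing from the TEAE tables and ungraded for severity and causality.

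Severity is low. The only size the documents support is 0.5 points of TEAE incidence per affected subject on active and 1.0 point on placebo. This assumes the planned arm sizes and that the subject has no other TEAE. The range of 1 to 5 points rests on an assumed 1% to 5% of subjects and on the contrast between full and no recording. That the effect is mostly non-differential rests on the blind holding.

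**What to change.** Reconcile 4.5.1 and 6.1.1 with 6.1 so that one recording rule applies at every site. In both places the optional sentence could become: *a post-treatment laboratory value judged clinically significant that is new or worse than at Screening will be recorded as an AE as defined in Section 6.1, unless it is a sign of an AE already recorded.* The last clause avoids double entry.

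Make sure that the data checks planned in Section 9.1 include a query for any post-treatment result marked CS with no matching AE record.

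The cost is two sentences in an amendment and, if not already planned, one data-management query. The downside is that AE counts may rise slightly in both arms.
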